2.4.4.2 Analyses of secondary efficacy endpoints

2.4.4.2.1 Average change from baseline to Week 16-24 in pre-bronchodilator FEV1

Main statistical model and adjustment of covariates

The key secondary efficacy endpoint, the average change from baseline to Week 16-24 in the pre-bronchodilator FEV1 will be analyzed using a mixed-effect model with repeated measures (MMRM) approach. Model-based average across Weeks 16, 20 and 24 will be compared between the treatment groups. The dependent variable is the change from baseline in pre-bronchodilator FEV1 at each time point. The model will include sex, baseline height, smoking history (current vs. former smoker), baseline FEV1 value, treatment group, visit and treatment-by-visit interaction, baseline FEV1-by-visit interaction, the baseline eosinophil strata, and region (pooled countries) as covariates. An unstructured correlation matrix will be used to model the within-patient correlations. Parameters will be estimated using restricted maximum likelihood method with the Newton-Raphson algorithm. No imputation will be performed on missing FEV1 measurements.

Descriptive statistics including number of patients, mean, standard error, and least squares (LS) means will be provided for each treatment group. Difference in LS means and the corresponding two-sided 95% CI and p-value will be provided for the comparison. Sample SAS code can be found below:

```
proc mixed data=fevldata method=reml;
  class usubjid sex csmoker trt01pn cntygr1 eosbgpln avisitn;
  model chg = sex height csmoker trt01pn trt01pn *avisitn FEV1bl
  FEV1bl* avisitn cntygr1 eosbgpln avisitn
           trt01pn*avisitn /ddfm=kr residual;
  repeated avisitn / subject=usubjid type=un;
  lsmestimate trt01pn*avisitn 'Tx wks 16-24 avg minus pbo wks 16-24 avg' 0 0
1 1 1 0 0 -1 -1 -1/ divisor=3;
  lsmeans trt01pn*avisitn / pdiff cl e;
  ods output LSMeans=LSMeans Diffs=Diffs LSMEstimates=LSMEstimates;
run;
```

If the above model fails to converge, the specification may be changed as follows: 1) use maximum likelihood estimation instead of restricted maximum likelihood method; 2) specify a different covariance structure to reduce the number of unknown parameters to be estimated, the path will be UN→TOEPH→TOEP→AR(1).

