MMRM model including measurements up to Week 52 will also be used to derive LS mean change at all time points measured. Differences in LS means, the corresponding 95% CI, and the p-value will be provided for comparison of SAR440340 versus placebo, along with descriptive statistics.

Similar analysis will be performed for the secondary efficacy population (high EOS group), without the baseline eosinophil strata in the model.

Sensitivity analyses

The following sensitivity analyses will be conducted to assess the robustness of the main model:

Analyses without imputation of the missing FEV1 data: these analyses will use the same MMRM model and estimation methods as specified above and include

- On-treatment analysis: In the case of premature discontinuation of study drug the analysis will include data up to 14 days after the last dose.

Analyses with imputation of the missing FEV1 data: these analyses will use the same MMRM model and estimation methods as specified above after missing data being imputed using the following methods

- Pattern-mixture multiple imputations: Missing pre-BD FEV1 values will be imputed multiple times using a regression model. The covariates to be included are sex, baseline height, smoking history (current vs. former smoker), baseline FEV1 value, treatment group, visit and treatment-by-visit interaction, baseline FEV1-by-visit interaction, the baseline eosinophil strata, and region (pooled countries). Forty imputations will be performed. For each imputation, the average change from baseline in pre-BD FEV1 to Weeks 16 to 24 will be analyzed. Statistical inference obtained from all imputed data will be combined using Rubin's rule.
- Control-based multiple imputations: Missing values will be imputed sequentially for each assessment time point using a regression model. Only estimate of the placebo group will be used to fit the MI models.

Similar analyses with imputation of the missing FEV1 data will be performed for the secondary efficacy population (high EOS group), without the baseline eosinophil strata in the model.

Technical details on the analyses with imputation of the missing FEV1 data are provided in [Appendix J](#).

Subgroup analysis

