rrU = exp(uclmean);  
run;
```

5. For control-based PMM-MI, we will replace the following command in Step 2 under “**data** ckrepimp”

```
lin=Intercept+mtx*txval+mst1*st1val+mreg1*reg1val+mreg2*reg2val+mx*xval;  
by
```

```
lin=Intercept+0*txval+mst1*st1val+mreg1*reg1val+mreg2*reg2val+mx*xval;
```

This way, we will use the control rate to impute the missing data.

6. For tipping-point analysis, we will replace the following command in Step 2 under “**data** ckrepimp”

```
lin=Intercept+mtx*txval+mst1*st1val+mreg1*reg1val+mreg2*reg2val+mx*xval;  
by
```

```
lin=Intercept+(mtx+delta)*txval+mst1*st1val+mreg1*reg1val+mreg2*reg2val+mx*xval;
```

where “delta” is a sequence of positive numbers representing the diminishing treatment effect for patients in the treatment group needing imputation. A table of p-values for the treatment effect in the analysis model with the imputed data and the “delta” value will be provided.

Change from baseline in FEV1

Pattern mixture model by multiple imputation

1. Partially impute data using Markov Chain Monte Carlo (MCMC) method to obtain 40 datasets with monotone missing pattern:

```
proc mi data=&DSTIN seed=&seed nimpute=40 out=monotone;  
  mcmc impute=monotone;  
  var base &chg_all;  
run;
```

where &chg_all includes change from baseline in FEV1 at all visits.

2. For each of the imputed dataset with monotone missing pattern, the remaining missing data will be imputed by a regression model

```
proc mi data=monotone seed=&seed nimpute=1 out=data_imp;
  by _imputation_;
  class trt01pn sex eosbgp1n cntygr1 endtrs1;
  var sex hgtbl eosbgp1n cntygr1 trt01pn endtrs1 base
      &chg_all;
  monotone reg;
run;
```

3. Analyze the 40 imputed datasets by the ANCOVA model described in [Section 2.4.4.2](#):

```
proc mixed data=data_imp method=reml;
  by _imputation_;
  class usubjid trt01pn sex cntygr1 eosbgp1n avisitn;
  model chg12 = trt01pn sex hgtbl cntygr1 eosbgp1n avisitn
      trt01pn*avisitn base base*avisitn /ddfm=kr residual;
  repeated avisitn / subject=usubjid type=un;
  lsmestimate trt01pn*avisitn 'Tx wks 16-24 avg minus pbo wks 16-24 avg' 0 0
1 1 1 0 0 -1 -1 -1 / divisor=3;
  lsmeans trt01pn*avisitn / pdiff cl e;
  ods output LSMeans=LSMeans_imp Diff=Diff_imp
LSMEstimates=LSMEstimates_imp;
run;
```

4. Apply Rubin's rule to combine analysis results:

```
proc sort data= LSMEstimates_imp;
  by trt01pn _imputation_;
run;

proc mianalyze data= LSMEstimates_imp;
  modeleffects estimate;
  stderr stderr;

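### Step 1 of the standard FEV1 multiple imputation in SAP Appendix J leaves out treatment, contrary to SAP Section 2.4.4.2.1; the resulting bias toward no effect is usually small, and the rest of the FEV1 code also needs aligning with the text

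*SAP*

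**What the plan says.** SAP Section 2.4.4.2.1 plans two sensitivity analyses of the key secondary endpoint that impute missing pre-bronchodilator FEV1. For the standard pattern-mixture version it states: "The covariates to be included are sex, baseline height, smoking history (current vs. former smoker), baseline FEV1 value, treatment group", followed by visit, the interactions, eosinophil strata and region. For the control-based version, only the placebo estimate is to be used in fitting the imputation models. Both are then analysed with the main MMRM, whose response is the change at each time point and whose covariates are given as: "The model will include sex, baseline height, smoking history (current vs. former smoker), baseline FEV1 value, treatment group, visit and treatment-by-visit interaction".

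Appendix J, under the FEV1 heading, gives the steps.

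- **Step 1** makes the missing pattern monotone: "mcmc impute=monotone" with "var base &chg_all;". It has no treatment variable and no BY statement.
- **Step 2** imputes the remaining (post-dropout) values by regression: "var sex hgtbl eosbgp1n cntygr1 trt01pn endtrs1 base", then the changes. Treatment is present and smoking is absent. `endtrs1` appears without a definition.
- **Step 3** reads: "Analyze the 40 imputed datasets by the ANCOVA model described in" Section 2.4.4.2, with "model chg12 = trt01pn sex hgtbl cntygr1 eosbgp1n avisitn". Smoking is absent and `chg12` is not defined.
- **Control-based version:** only step 2 changes, so step 1 is reused. Smoking is absent here too.

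**The concern.** An imputation model that leaves out treatment draws missing values in both arms from a common distribution. Filled values in the drug arm move toward the pooled mean, and those in the placebo arm move the other way. The estimated difference then shrinks for a reason unrelated to the missing-data assumption under test. A sensitivity analysis should differ from the main model only in that assumption.

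The main text never describes the MCMC step and sends the reader to Appendix J for technical detail, so a programmer has no other instruction for it.

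Intermittent gaps are foreseeable. The Schedule of Activities moves a missed spirometry to the following visit. In SAP Table 6 the pre-bronchodilator windows for Weeks 16, 20 and 24 close on Days 126, 154 and 182, while the next visits have target Days 127, 155 and 183. A make-up test on its target day therefore falls one day outside the window of the missed visit.

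**Working it through.** **Inputs from the documents.** SD 0.3 L, difference 0.12 L, 170 per arm, 1:1 allocation, 15% missing at Week 24, two-sided 5% (Protocol Section 9.2, SAP Section 1.3). There are seven post-baseline pre-bronchodilator visits to Week 24 (Weeks 2, 4, 8, 12, 16, 20 and 24; SAP Table 6).

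**Assumed, because the documents give none of these.** Intermittent gaps of 5%, 10% or 20% per visit; within-patient correlation 0.4-0.8, either compound symmetric or autoregressive; effect constant from Week 2, ramped, or starting at Week 16.

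**Planned figure.** n = 170 × 0.85 = 144.5 per arm. SE = 0.3 × √(2/144.5) = 0.0353 L. Power = Φ(0.12/0.0353 − 1.96) = Φ(1.44) = 92.5%, against the protocol's 92.6%. The least significant difference is 0.0695 L, against the stated 0.07 L. Both reproduce.

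**What step 1 does to one filled visit.** Let S be the within-arm covariance and d the vector of arm differences by visit. Pooling two equal arms gives covariance T = S + dd′/4. A gap at visit j is filled by regression on the other visits O, so the arm difference in filled values is T_jO T_OO⁻¹ d_O, to be compared with d_j.

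Worked case, compound symmetry 0.4 with a constant effect:
- Between-arm term: 0.12²/4 = 0.0036.
- T has common off-diagonal 0.4 × 0.09 + 0.0036 = 0.0396 and residual 0.6 × 0.09 = 0.054.
- Weight per visit: 0.0396/(0.054 + 6 × 0.0396) = 0.1358.
- Six visits: the filled value keeps 6 × 0.1358 = 81.5% of the effect.

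The other observed visits carry treatment information, so the effect in a filled gap is reduced, not erased. Averaged over a gap at Week 16, 20 or 24, the share kept is:

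| Correlation | Constant from Week 2 | Starts at Week 16 |
|---|---|---|
| CS 0.4 | 0.815 | 0.332 |
| CS 0.6 | 0.906 | 0.386 |
| CS 0.8 | 0.962 | 0.465 |
| AR 0.8 | 0.922 | 0.774 |

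The extremes over all settings are 0.332 and 0.962.

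**Effect on the Week 16-24 difference.** Proportional loss = gap rate × (1 − share kept).
- 5% gaps: 0.05 × 0.038 = 0.2% to 0.05 × 0.668 = 3.3%; expected estimate 0.116-0.120 L.
- 10% gaps: 0.4% to 6.7%; 0.112-0.120 L, so at most about 8 mL.
- 20% gaps: 0.8% to 13%; 0.104-0.119 L.

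**Simulation.** 60 runs per setting, compound symmetry 0.6, 15% dropout, treatment kept in step 2. Pooled minus by-arm filling, at 5%, 10% and 20% gaps:
- constant effect: −0.0004, −0.0009 and −0.0021 L;
- effect from Week 16: −0.0026, −0.0050 and −0.0104 L.

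These losses are somewhat below the formula. One reason is that in a seven-visit simulation a Week 24 gap has no later visit and so cannot be intermittent.

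**Control-based version.** The rule in Section 2.4.4.2.1 is placebo-only filling, which replaces T by S.
- CS 0.4, constant effect: weight 0.036/(0.054 + 6 × 0.036) = 0.1333, share kept 6 × 0.1333 = 80.0%, against 81.5% for pooled filling.
- CS 0.4, effect from Week 16: 26.7%, against 33.2%.

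Pooled filling kept slightly more of the effect than placebo-only filling in every setting tried.

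**The case against.** Three counter-arguments have weight.

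**The code may be only illustrative.** Appendix J opens with a note that its code is explanatory and that covariates follow the main text. If that covers the FEV1 part, a programmer would add smoking anyway. However, the note stands under the exacerbation-rate heading, is not repeated for FEV1, and speaks only of covariates. It does not clearly reach an MCMC step that the main text never mentions, and it does not reach a response name.

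**Step 3 is the MMRM in all but name.** The code has visit, treatment-by-visit and baseline-by-visit terms, an unstructured repeated statement and the Week 16-24 contrast. Section 2.4.4.2.1 asks for the same MMRM. This stands: `chg12` and ANCOVA are labelling errors, not evidence of a different analysis.

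**Little depends on it.** The main analysis imputes nothing, and SAP Section 2.4.4.4 treats all p-values as nominal. This also stands, and it sets the priority.

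A reader might infer that every discrepancy pulls toward no effect, or that both imputation analyses understate the difference. The documents do not support either reading. Omitting a baseline covariate in a 1:1 randomized trial has no such direction, and an undefined variable name has none. For the control-based version, the benchmark is placebo-only filling, which attenuates slightly more than the pooled step.

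**Conclusion.** The point holds for step 1 of the standard pattern-mixture imputation. As printed, it omits treatment where Section 2.4.4.2.1 includes it, and this biases that one sensitivity analysis toward no effect. The loss is about 0.2-3.3% of 0.12 L at 5% intermittent gaps and 0.4-6.7% at 10%. It becomes material only if gaps are frequent and the effect starts late. These sizes rest wholly on the assumed gap rate, correlation and onset shape.

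Post-dropout values in the standard method are imputed with treatment in the model. The main MMRM and the on-treatment analysis are untouched. In the control-based analysis, the reused step is a departure from the stated rule, without extra attenuation.

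The missing smoking term, `chg12`, ANCOVA and `endtrs1` are specification and reproducibility defects with no known direction of bias. Overall this is a low-priority correction, worth making because it is nearly free.

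**What to change.** In Appendix J, FEV1 part:

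1. Standard method, step 1: run by `trt01pn`, or add a 0/1 treatment variable to the VAR list. Running step 1 within arm removes the attenuation, and the expected estimate returns to 0.12 L.
2. Control-based method: do not simply inherit that change, because filling drug-arm gaps from the drug arm is not placebo-only. Either give a separate step 1 that follows Section 2.4.4.2.1, or state there that intermittent gaps are filled within arm and only post-dropout values come from placebo.
3. Add `csmoker` to steps 2 and 3 and to the control-based code.
4. Replace `chg12` with the by-visit change, and call the model an MMRM.
5. Define or delete `endtrs1`.
6. State whether the explanatory note covers the FEV1 code.

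The cost is a few lines of code and one or two sentences of text. No data collection, sample size or main analysis changes.
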